## 11.2. Analysis Sets

#### 11.2.1. Full Analysis Set

The FAS will include all subjects enrolled in the study who received at least 1 dose of U3-1402.

## 11.2.1.1. Dose-Limiting Toxicity Evaluable Set

The DLT-evaluable set will include all subjects enrolled in the study who received at least 1 dose of U3-1402, with the exception of those subjects for whom DLT evaluation could not be adequately conducted.

#### 11.2.1.2. Safety Analysis Set

The safety analysis set will include all subjects enrolled in the study who received at least 1 dose of U3-1402.

#### 11.2.1.3. Pharmacokinetic Analysis Set

The PK analysis set will include all subjects enrolled in the study who received at least 1 dose of U3-1402 and had measurable serum concentrations of U3-1402, total anti-HER3 antibody or MAAA-1181a.

## 11.3. Study Population Data

Disposition and reasons for ending the treatment and discontinuing from the study will be summarized and listed for subjects in the enrolled analysis set.

Demographic and baseline characteristics such as age, sex, race, ethnicity, baseline ECOG PS, histology, cancer stage, best response to prior chemotherapy, lines of prior regimens, and prior treatment type will be summarized for the FAS, and safety analysis set. If 2 analysis sets within a part of the study are identical to each other, the table will be presented only once.

## 11.4. Statistical Analysis

## 11.4.1. Efficacy Analyses

Efficacy endpoints will include ORR (the sum of CR and PR rates); DCR (the sum of CR rate, PR rate, and SD rate), DOR, CBR, TTR, PFS, OS, and percent change in target lesion(s). Tumor responses will be assessed by an Investigator and an independent central imaging CRO according to RECIST 1.1.

The efficacy endpoints will be listed and summarized. For ORR and DCR and CBR, point estimates 2-sided 95% exact binomial confidence intervals will be provided. Time to event variables including PFS, OS, TTR, and DOR will be summarized descriptively using the Kaplan-Meier method. PFS is defined as the time from the date of the first dose to the earlier of the dates of the first objective documentation of radiographic PD or death due to any cause. Censoring rules for the PFS analysis will be specified in the SAP.

Descriptive statistics for the best percent change from baseline in the sum of diameters of measurable tumors will be provided. A waterfall plot of the best percent change in the sum of diameters for each subject will be presented.

#### 11.4.2. Pharmacokinetic Analyses

PK analyses will be performed on the PK analysis set. Serum concentration-time data for U3-1402, total anti-HER3 antibody and MAAA-1181a will be listed, plotted, and summarized using descriptive statistics by cohort at each point and in study period.

PK parameters of U3-1402, total anti-HER3 antibody and MAAA-1181a will be listed and summarized using descriptive statistics.

The comparison of the PK profile between each region (Japan and the US) will also be assessed.

Serum concentration data will be used to perform a population PK modeling. The influences of intrinsic or extrinsic factor will be assessed in the population PK analysis. If performed, results of population PK analyses will be reported separately (ie, not in the Clinical Study Report).

#### 11.4.3. Pharmacodynamic Analyses

Not applicable.

#### 11.4.4. Biomarker and Exploratory Analyses

Explorative analyses for biomarkers will be listed and summarized using descriptive statistics.

#### 11.4.5. Safety Analyses

Safety endpoints will include TEAEs, SAEs, AESIs, clinical laboratory measurements, vital sign measurements, ECG recordings, physical examination findings, ECHO/MUGA findings, and ophthalmologic findings. In the Dose Escalation Part, the incidence of DLTs will also be evaluated.

Safety analyses in general will be descriptive and will be presented in tabular format with the appropriate summary statistics. In the Dose Escalation Part, the number of DLTs identified among the DLT-evaluable subjects in the DLT-evaluable set will be listed and summarized by cohort. Additional details regarding safety analyses will be described in the SAP.

#### 11.4.5.1. Adverse Event Analyses

A TEAE is defined as an AE that emerges or worsens during the on-treatment period. The on-treatment period is defined as from the start date of study treatment (inclusive) to 47 days after the end date of study treatment (inclusive). SAEs starting or worsening after the on-treatment period, if reported as related to the study treatment, are also considered TEAEs. The AE summary will only include TEAEs.

The number and percentage of subjects reporting TEAEs will be tabulated by the worst NCI-CTCAE grade, System Organ Class (SOC), and preferred term.

Similarly, the number and percentage of subjects reporting treatment-emergent SAEs will be tabulated, as well as TEAEs/SAEs considered related to U3-1402.

A by-subject AE (including TEAE) data listing will be provided including, but not limited to, verbatim term, preferred term, SOC, NCI-CTCAE grade, and relationship to study drug.

Deaths, other SAEs, and other significant AEs, including those leading to permanent discontinuation from U3-1402, will be listed.

#### 11.4.5.2. Clinical Laboratory Evaluation Analyses

Descriptive statistics will be provided for selected clinical laboratory test results (hematology and chemistry) and changes from baseline by scheduled time of evaluation, including the EOT visit, maximum post-treatment value, and minimum post-treatment value.

Abnormal laboratory results will be graded according to NCI-CTCAE version 5.0, if applicable. A shift table, presenting the 2-way frequency tabulation for baseline and the worst post-treatment

value according to the NCI-CTCAE grade, will be provided for selected clinical laboratory tests. Abnormal clinical laboratory test results that are deemed of clinical significance or of Grade 3 or 4 will be listed.

### 11.4.5.3. Vital Sign Analyses

Descriptive statistics will be provided for the vital signs measurements and changes from baseline by scheduled time of evaluation, including the EOT visit and the maximum and minimum post-treatment values.

### 11.4.5.4. Electrocardiogram Analyses

Descriptive statistics will be provided for ECG parameters and changes from baseline by scheduled time of evaluation, including the EOT visit and the maximum post-treatment value. In addition, the number and percentage of subjects with ECG interval values meeting the criteria will be tabulated (eg, QTc  $\leq$ 450 ms,  $\geq$ 450 to  $\leq$ 480 ms,  $\geq$ 480 ms to  $\leq$ 500 ms, and  $\geq$ 500 ms).

The QT intervals will be corrected for heart rate by Fridericia's formula (QTcF =  $QT/[RR]^{1/3}$ ).

Relationship between drug concentrations and QTcF may be analyzed. This analysis will be performed for subjects across all dose levels.

## 11.4.5.5. Exploratory Safety Analyses

Not Applicable.

#### 11.4.5.6. Other Safety Analyses

All other safety variables (physical examination findings including ECOG PS, ECHO/MUGA findings, and ophthalmologic findings) will be listed.

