## 4.1.3. Inclusion Criteria for Dose Expansion Part

- 1. Has a pathologically documented advanced/unresectable or metastatic breast cancer.
- 2. Has documented HER3-positive (HER3-high or HER3-low) disease assessed by IHC assay by the central laboratory from archival tumor tissue or a screening tumor fresh biopsy sample.
- 3. Is able to submit a fresh tumor biopsy sample prior to starting study treatment. (If subjects have already submitted fresh tumor biopsy sample for HER3 expression, resubmission is not necessary.)
- 4. Has documented HER2-negative expression according to American Society of Clinical Oncology College of American Pathologists (ASCO-CAP) guidelines.
- 5. Has documented HR (estrogen and/or progesterone receptor) positive disease with exception of the TNBC cohort (see inclusion criterion #17 below).
- 6. Is refractory to or intolerant to standard treatment, or for whom standard treatment is no longer available.
- 7. With the exception of the TNBC cohort (see inclusion criterion #18 below), has received ≥2 and ≤6 prior chemotherapeutic regimens for breast cancer, ≥2 of which were administered for treatment of advanced/unresectable or metastatic disease. At least 1 prior chemotherapeutic regimen must have included a taxane (eg, paclitaxel, docetaxel), administered in the neoadjuvant, adjuvant, or advanced setting.
- 8. Male or female subjects aged  $\geq$ 20 years in Japan,  $\geq$ 18 years in the US.
- 9. Has an ECOG PS 0-1, with no deterioration over the previous 2 weeks.
- 10. Has LVEF ≥50% by either ECHO or MUGA within 28 days prior to enrollment.
- 11. Has adequate bone marrow reserve and organ function within 7 days prior to enrollment, defined according to the following:

Item	Laboratory value
Platelet count	≥100 000/mm 
Hemoglobin (Hb)	≥9.0 g/dL
Prothrombin time (PT) or PT- international normalized ratio (INR) and partial thromboplastin time (PTT)	≤1.5 × ULN, except for subjects on coumarin-derivative anticoagulants or other similar anticoagulant therapy, who must have PT-INR within therapeutic range as deemed appropriate by the Investigator.
Absolute neutrophil count (ANC)	≥1500/mm³
Creatinine	≤1.5 × ULN, or creatinine clearance ≥50 mL/min as calculated using the Cockcroft-Gault equation
AST/ALT	$\leq$ 3 × ULN (if liver metastases are present, $\leq$ 5 × ULN)
Total bilirubin	≤1.5 × ULN (<3 × ULN in the presence of documented Gilbert's Syndrome [unconjugated hyperbilirubinemia] or liver metastases)

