	Grade 4 (Life-threatening consequences; urgent intervention indicated)	Delay dose until resolved to ≤Grade 2 or baseline, then reduce U3-1402 by 1 dose level and resume.  Consider transfusion according to institutional guidelines.
Platelet count decreased	Grade 3 (Platelet <50 - 25 × 10  /L)	Delay dose until resolved to ≤Grade 1, then:  If resolved in ≤14 days, resume U3-1402.  If resolved in >14 days, U3-1402 may be resumed.  Consider reducing U3-1402 by 1 dose level.  Consider platelet transfusion according to institutional guidelines.
	Grade 4 (Platelet <25 × 10  /L)	Delay dose until resolved to ≤Grade 1, then reduce U3-1402 by 1 dose level and resume.  Consider transfusion according to institutional guidelines.
Lymphocyte Count Decreased	Grade 4 (<0.2 × 10  /L)	Delay dose until resolved to ≤Grade 2, then: If resolved in ≤14 days, resume U3-1402. If resolved in >14 days, reduce U3-1402 by 1 dose level and resume.
Cardiac disorders		
Heart failure	Grade ≥2 (Symptoms with moderate activity or exertion)	Cardiologist consult as necessary.  Delay dose until resolved to ≤Grade 1, then reduce U3-1402 by 1 dose level.
Ejection fraction decreased	Decrease in LVEF 10% to 20% (absolute value), but LVEF >45%	Continue treatment with U3-1402.
	LVEF 40% to ≤45% and decrease is <10% (absolute value) from baseline	Continue treatment with U3-1402. Repeat LVEF assessment within 3 weeks.

Table 5.2: Dose Delay Criteria and Dose Reduction for U3-1402 (Continued)

	Worst Toxicity NCI- CTCAE Version 5.0 Grade (unless otherwise specified)	Schedule Modification for U3-1402
	LVEF 40% to ≤45% and decrease is ≥10% to 20% (absolute value) from baseline	Delay U3-1402 dosing. Repeat LVEF assessment within 3 weeks. If LVEF has not recovered to within 10% (absolute value) from baseline, discontinue subject from study treatment.
	LVEF <40% or >20% drop from baseline	Delay U3-1402 dosing.  Repeat LVEF assessment within 3 weeks; if LVEF <40% or >20% (absolute value) drop from baseline is confirmed, discontinue U3-1402.  Cardiologist consult as necessary.

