#### Within 3 days prior to infusion

- Perform a complete physical examination and record weight.
- Obtain vital sign measurements (systolic and diastolic blood pressure and pulse rate, body temperature and SpO2).
- Assess functional status using the ECOG PS Scale (Section 17.3).
- Perform either ECHO or MUGA (LVEF). Investigators must ensure results of ECHO/MUGA are available for review prior to dosing on corresponding cycle visits. Repeat ECHO/MUGA assessments are not required in the event of dose delays that occur after examination if there are no abnormal findings. ECHO or MUGA may be repeated per Investigator discretion.
- Obtain blood samples for safety laboratories (Section 8.8).

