### Within 3 days prior to infusion

- Perform a complete physical examination and record weight.
- Assess functional status using the ECOG PS Scale (Section 17.3).
- Obtain vital sign measurements (systolic and diastolic blood pressures, pulse rate, body temperature, and SpO2).
- Perform either ECHO or MUGA (LVEF). Investigator must ensure results of ECHO/MUGA are available for review prior to dosing on corresponding cycle visits. If there is a delay after an ECHO/MUGA assessment with no clinically significant findings, then repeat assessments are not required but may be repeated per Investigator discretion.
- Obtain blood samples for safety laboratories (Section 8.8).

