## 8.2. Adverse Event Collection and Reporting

All clinical AEs occurring after the subject signs the ICF and up to F/U visit after the last dose of study drug (ie, the follow-up period), whether observed by the Investigator or reported by the subject, will be recorded on the Adverse Event Case Report Form (CRF) page. Medical conditions (including clinical laboratory values/vital signs that are out of range) that were diagnosed or known to exist prior to Informed Consent will be recorded as part of medical history.

All AEs, AESIs, events of overdose, and SAEs are to be reported according to the procedures in Section 8.5.

All clinical laboratory results, vital signs, and ECG results or findings should be appraised by the Investigator to determine their clinical significance. Isolated abnormal clinical laboratory results, vital sign findings, or ECG findings (ie, not part of a reported diagnosis) should be reported as AEs if they are symptomatic, lead to study drug discontinuation, dose reduction, require corrective treatment, or constitute an AE in the Investigator's clinical judgment.

At each time point, the Investigator will determine whether any AEs have occurred by evaluating the subject. Adverse events may be directly observed, reported spontaneously by the subject or by questioning the subject at each time point. Subjects should be questioned in a general way, without asking about the occurrence of any specific symptoms. The Investigator must assess all AEs to determine seriousness, severity, and causality, in accordance with the definitions in Section 8.4. The Investigator's assessment must be clearly documented in the study site's source documentation with the Investigator's signature.

Always report the diagnosis as the AE or SAE term. When a diagnosis is unavailable, report the primary sign or symptom as the AE or SAE term with additional details included in the narrative until the diagnosis becomes available. If the signs and symptoms are distinct and do not suggest a common diagnosis, report them as individual entries of AE or SAE.

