# 8.3.1. Cardiotoxicity (Cardiac-related Events Including QT Prolongation and LVEF Decreased)

LVEF will be measured by either ECHO or MUGA scan. All ECHOs/MUGAs must be evaluated by the Investigator or a delegated physician for monitoring cardiac function. The same modality (ECHO or MUGA) should be used for the subject throughout the study. In addition, standard ECG parameters will be measured, including RR, PR, and QT intervals, and QRS duration. All ECGs must be evaluated by Investigator or a delegated physician for the presence of abnormalities. In this study, cTnI testing will be used as an exploratory biomarker in parallel with standard clinical assessments of cardiac function (eg, ECHO/MUGA and ECG).

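### LVEF, a named adverse event of special interest measured before each infusion from Cycle 2, is planned only as a listing; by-cohort LVEF tables should be added

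*Combined protocol and SAP*

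**What the plan says.** Protocol Section 11.4.5.6 covers LVEF in one sentence: "All other safety variables (physical examination findings including ECOG PS, ECHO/MUGA findings, and ophthalmologic findings) will be listed".

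Elsewhere the protocol gives LVEF more weight:

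- Section 8.3.1, on adverse events of special interest (AESIs), is titled "Cardiotoxicity (Cardiac-related Events Including QT Prolongation and LVEF Decreased", so QT and LVEF sit under one heading.
- Section 3.1.7 makes LVEF below 40%, or a drop of more than 20% from baseline, a DLT.
- Table 5.2 (Section 5.4.2) has four LVEF rows. For "Decrease in LVEF 10% to 20% (absolute value), but LVEF >45" per cent, dosing goes on. For "LVEF 40% to ≤45% and decrease is ≥10% to 20% (absolute value) from baseline", dosing is delayed and LVEF repeated.
- Entry to the Dose Expansion Part requires: "Has LVEF ≥50% by either ECHO or MUGA within 28 days prior to enrollment".
- LVEF is then measured within 3 days before infusion. For Cycle 2 (Section 6.4.10) the instruction is: "Perform either ECHO or MUGA (LVEF). Investigators must ensure results of ECHO/MUGA are available for review prior to dosing on corresponding cycle visits". Cycle 3 (Section 6.4.15) says: "Investigator must ensure results of ECHO/MUGA are available for review prior to dosing on corresponding cycle visits". Section 6.4.21 extends this to Cycle 4 and all later cycles, and Section 6.7 adds the end-of-treatment visit.

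On adverse event recording, Section 8.2 says that isolated laboratory, vital sign or ECG findings "should be reported as AEs if they are symptomatic, lead to study drug discontinuation, dose reduction, require corrective treatment", or are adverse events in the Investigator's judgment. ECHO/MUGA is not named in that sentence.

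**The concern.** Safety is a primary objective in all three parts (Section 2.1.1), and about 60 subjects are randomized between 4.8 and 6.4 mg/kg. That is the best setting in the study for seeing whether a cardiac effect depends on dose. LVEF is a repeated continuous measurement with a baseline, so it suits a by-visit summary and a worst-value table as well as QTcF does. The protocol tabulates QTcF and only lists LVEF, and gives no reason for the difference.

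The practical risk is a drift in LVEF that stays in the range where nothing is done to dosing. Each such fall would be one line in a long listing. Unless someone counts those lines by dose, the planned tables would not show the pattern.

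**Working it through.** The protocol states no figure for this point, so there is none to reproduce. The check sets the planned analyses side by side and then follows one LVEF fall through the recording rules.

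**1. Planned analyses (Section 11.4.5)**

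| Variable | Summary statistics and change from baseline | Categories or shifts |
|---|---|---|
| Laboratory tests (11.4.5.2) | Yes | Shift from baseline to worst grade |
| Vital signs (11.4.5.3) | Yes, with maximum and minimum | None named |
| ECG (11.4.5.4) | Yes, with maximum | Counts in QTc bands |
| LVEF (11.4.5.6) | No | No |

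**2. Can a fall occur with no dose action?** The band needs a drop of at least 10 points that leaves LVEF above 45%. Baseline must therefore exceed 45 + 10 = 55%. Entry requires 50% or more, so the band is reachable. Two illustrative subjects:

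- Baseline 65%, later 47%: drop 65 − 47 = 18 points, LVEF above 45%, dosing goes on.
- Baseline 60%, later 44%: drop 60 − 44 = 16 points, LVEF between 40% and 45%, dosing is delayed.

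The larger of these two falls is the one with no dose action.

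**3. Does the first subject reach a planned table?**

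- *DLT table.* No. It covers Cycle 1 of the Dose Escalation Part, and the LVEF criterion there is below 40% or a drop of more than 20%.
- *Dose-action route.* No. Section 5.4 has interruptions and modifications entered on the adverse event page as well as the drug administration page, but here there are none.
- *Section 8.2 criteria.* With no symptoms, discontinuation, dose reduction or corrective treatment, only Investigator judgment is left. That holds if the rule is applied by analogy, since it does not name ECHO/MUGA.
- *TEAE tables (11.4.5.1).* Only if the Investigator recorded an adverse event. These tables are by worst grade, system organ class and preferred term; no AESI table is named.
- *LVEF listing.* Yes.

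**4. What a by-dose count would tell.** Assume 30 subjects per randomized dose (60 / 2).

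- With 0 of 30 falls, the exact two-sided 95% upper limit is 1 − 0.025^(1/30) = 11.6%.
- With 3 of 30, the exact (Clopper-Pearson) interval is 2.1% to 26.5%.
- The chance of at least one fall is 1 − (1 − p)^30. The documents give no rate, so p is an assumption: 59.9% at p = 3%, 78.5% at 5%, and 95.8% at 10%.

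A count per dose group would be imprecise but informative. These figures describe how such a table would perform. They do not measure under-recording.

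**The case against.** The strongest reply is that the protocol leaves the detail to the SAP. Section 11.4.5 names ECHO/MUGA findings as a safety endpoint, says safety results will generally be tabulated, and defers further detail; Section 11.6 assigns methods and table shells to the SAP. No SAP text was available, so an LVEF table may already be planned. This stands as a limit on the point but does not remove it. The only instruction specific to LVEF is a listing, and a SAP that followed it would comply without any table.

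A second reply is that LVEF falls will be recorded anyway. AESIs are collected by targeted questionnaire (Section 8.3) and reported in the CRF (Section 8.5). Every ECHO/MUGA must be evaluated by the Investigator or a delegate. Table 5.2 lists the 10 to 20 point fall as a toxicity, and Section 5.4 limits dose modification to drug-related TEAEs, which suggests that such a fall is seen as a possible TEAE. This is fair, and some falls will be captured. But Section 8.3.1 gives no LVEF threshold for the AESI, so capture still rests on judgment.

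Three stronger readings are tempting and are not supported:

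- *That 4.8 and 6.4 mg/kg cannot be compared on LVEF.* The listing would hold subject-level values, so counts by dose can be derived. What is missing is a planned summary.
- *That the number of hidden cases can be estimated.* A probability from an assumed rate says how often falls occur, not how often they go unrecorded. The documents give neither rate.
- *That a cardiac signal is expected.* Myocardial necrosis or degeneration was reported in a rat that died at the highest dose, a moribund monkey on weekly dosing, and a moribund monkey given the payload alone (Section 1.2.2.4). The 12-week Q3W monkey study reports no cardiac finding among its major toxicities. Section 1.4 lists an LVEF decrease as a potential risk, not an identified one.

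**Conclusion.** The point holds as a shortfall in planned safety analysis. The protocol treats an LVEF decrease as an AESI, a DLT criterion and a dosing criterion, and measures LVEF at every cycle from Cycle 2, but plans no table of it by dose. The gap matters most for asymptomatic falls of 10 to 20 points with LVEF above 45%, whose route into the TEAE tables is Investigator judgment.

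Its size is limited. It concerns one safety variable, loses no data, and touches no sample size, decision rule or efficacy result. The conclusion assumes that the sentence specific to LVEF governs over the general remark about tabular presentation, and that the SAP does not already supply the table. If it does, only the protocol wording needs aligning. The change is worth making because it is nearly free and serves a primary objective.

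**What to change.** In Section 11.4.5.6, or in the SAP before database lock, add for LVEF:

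1. Descriptive statistics of LVEF and of change from baseline, by cohort, at each scheduled visit and at end of treatment.
2. The number and percentage of subjects by cohort, classified by worst post-baseline LVEF with the existing Table 5.2 cut-offs, assigned in this order:
   - below 40%, or a drop of more than 20 points;
   - 40% to 45% with a drop of 10 points or more;
   - 40% to 45% with a drop of less than 10 points;
   - above 45% with a drop of 10 to 20 points;
   - none of these.

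Show subjects with no post-baseline LVEF separately, so that the denominators are clear; Section 11.1 already limits change from baseline to subjects with both values. Keep the listing.

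The cost is one or two tables from data already collected. The cut-offs serve only as reporting categories, and no dosing rule, visit or sample size changes.
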